Group 2 included 30 patients with the same diet, but adding linseed oil for 6 days a week in an amount of 13g/day. And in group 3, 30 patients were included in the same dietary regimen that group 1, adding flaxseed flour to their diet for 6 days a week, providing 32g of flaxseed per day. They concluded that in the 3 groups there was a reduction in blood glucose, however the decrease in glucose in Fasting reported by group 3 had better target figure achievements (Tharwat., 2017).

In a systemic review in 2018 Mohammadi et al, evaluated 25 randomized clinical trials, presenting a significant association between flaxseed supplementation and a reduction in blood glucose. It is worth mentioning that this relationship was more significant in the groups in trials that used ground flaxseed and reported an administration between 4 to 14 grams. (Mohammad., et al, 2018)

Hasaniani et al in 2019 conducted a randomized, controlled clinical trial with 57 patients with Diabetes Mellitus type 2. He divided his population into 2 groups. One group was prescribed 200g of natural yogurt in their diet and the other. Another group was also prescribed 200g natural yogurt with 30g of flaxseed added for 8 weeks documented a significant reduction in hemoglobin A1c ($p=0.001$) compared to the control group (Ha-saniani, 2019). In another study, Nowak concluded that regular consumption of flax seed improves the lipid profile by reducing triglycerides and total cholesterol and increasing HDL cholesterol (Nowak & Jeziorek., 2023)

5. Design of the research methodology.

Randomized clinical trial (case-control).

The sample will be recruited by self-selection.

The total number of recruited participants will be divided into two groups (A and B).

The control group will be given a talk nutritional education using the healthy eating plate and the intervention group will be instructed on supplementation with flaxseed (16 gr of flaxseed/day for three months) and also a nutritional education talk using the plate of good eating.

Once they sign the legal informed consent for participation, a clinical history will be applied where

Sociodemographic variables such as age, sex, occupation and marital status will be

asked. Clinical characteristics such as time since the disease has been on the disease, type of current diabetes treatment, control and comorbidities will also be asked. These variables will be collected at the beginning of the research and only once during the study.

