They will be given verbal instructions to continue with the treatment established by the treating physician, they will be given nutritional guidance with the help of the healthy eating plate and they will be provided with a pamphlet with the instructions. written and photographed on how to consume flaxseed and its benefits.

Phase 3.

Administration of flaxseed

Researchers will purchase, package, and provide flaxseed powder to members of group B. Flaxseed will be delivered in packages with 16 gr of ground flaxseed each, which will be given to patients for their daily consumption (a tablespoon of 8

gr of flaxseed in the morning snack and 8 gr of flaxseed in the afternoon snack)

(late). You will be provided with brochures with images explaining how to consume it and how the glass should look when finished. Various forms of consumption of the powder will also be provided to avoid getting bored with the taste and consistency. from dust.

Phase 4.

Surveillance and monitoring.

Daily contact will be maintained with participants via WhatsApp in order to remind them to take flaxseed.

and also to find out if they have any adverse symptoms (abdominal distension, flatulence, gas, diarrhea, etc.), as well as to resolve doubts and ask if they should start taking some vitamins, minerals or medications.

Both groups will be given a 24-hour recall and a food frequency questionnaire. every 15 days. The food consumption of both groups will be analyzed according to its nutritional content (energy, macro and micronutrients) and each nutrient will be used as a nutritional variable that can influence the control of the biochemical markers.

Phase 5.

Data analysis.

Statistical analysis will be performed using the IBM SPSS Statistics program version 24, in which it will be performed descriptive statistics and for group comparisons different tests will be performed depending on the nature of the variables. The comparison between the values measured at the beginning and the values measured after 3 months in each group will be performed using the paired t test and will be

considered statistically significant when $p < 0.05$.

Inclusion criteria:

- ÿ Patients entitled to who attend the “Presidente” Regional Nutrition outpatient clinic Benito Juárez” diagnosed at most one year ago and who agree to participate in the study by signing the informed consent.
- ÿ Patients diagnosed with uncontrolled Diabetes Mellitus evidenced by biochemical markers, den-

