within a maximum of 1 month of validity, (fasting blood glucose greater than 140 and glycosylated hemoglobin greater than (6.5%).
- ÿ Patients with regular attendance at the outpatient clinic for at least 3 consecutive months.

Exclusion criteria:

- ÿ Patients diagnosed with chronic kidney disease undergoing renal function replacement therapy.
- ÿ Patients who already consume enough fiber and omega 3, as evidenced by the application of a reminder of 24 hours and a food frequency questionnaire.
- ÿ Pregnant or
breastfeeding women.
- ÿ Patients in
menopause.
- ÿ Patients with glucose disorders secondary to autoimmune diabetes, thyroid diseases or insulin-producing tumors.
- ÿ Patients with a medical history of poor drug adherence.
- ÿ Patients with adequate glycemic control evidenced by clinical laboratory tests for at least 2 months.
- ÿ Patients who cannot read or write.

ÿ Patients who do not have a means of contact for follow-up.

Elimination criteria:

ÿ Patients who do not agree to participate in the study. ÿ Data collection instrument with incomplete items.

ÿ People who voluntarily withdraw from the study at any time. ÿ If the patient has surgery during the study.

ÿ Patient who during the study begins to consume any type of supplement (vitamins, minerals, omega 3).

ÿ Patient who stops consuming flaxseed during the study.

8. Experience of the principal investigator and co-investigators in this type of research.

(maximum)

The principal investigator has participated in different research projects in the area, both as a collaborator and as principal investigator:

-Collaborating researcher. Faculty of Nutrition. Universidad Veracruzana. **“Evaluation of waist circumference in fifth period students of proposal 3 and 4 as a risk factor for developing metabolic syndrome”**. Faculty of Nutrition. Xalapa, Universidad Veracruzana, Mexico. 2010. SATISFACTORILY COMPLETED

-Collaborating researcher. Cooperation with the Coordination of the Master's Degree in Food and Nutritional Security.

“Influence of maternal nutrition on the programming of fetal adipose tissue development”. Faculty of Nutrition. Universidad Veracruzana. 2011. SATISFACTORILY COMPLETED

-Collaborating Researcher. **“Influence of physical activity on biochemical and vascular factors determining endothelial dysfunction in postmenopausal women”**. Sant Joan de Reus University Hospital, Tarragona, Spain, 2012. SATISFACTORY COMPLETED

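### The protocol does not say whether group A receives the daily WhatsApp contact; its wording leans towards group B only, which would mix flaxseed with daily attention and closer surveillance.

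*Protocol*

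**What the plan says.** Section 7, Phase 4 (Surveillance and monitoring) opens with: "Daily contact will be maintained with participants via WhatsApp in order to remind them to take flaxseed". The sentence continues with a check for gastrointestinal symptoms and ends "as well as to resolve doubts and ask if they should start taking some vitamins, minerals or medications". The English is awkward; I take the last part to mean asking whether the patient has started any of these.

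Phase 3 limits the product to one arm: "Researchers will purchase, package, and provide flaxseed powder to members of group B". The next paragraph of Phase 4 turns to both arms by name: "Both groups will be given a 24-hour recall and a food frequency questionnaire", every 15 days. The description of group A in Phase 2 lists continued treatment from the treating physician and healthy-eating-plate guidance. It mentions no daily contact.

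Three other places bear on the point:
- Section 10 (Management of potential risks) repeats the daily contact for safety and again refers to participants without naming an arm. Its risk table describes the monitoring as directed at health problems due to flaxseed.
- The exclusion criteria rule out any patient who cannot be reached for follow-up, in either arm.
- The elimination criteria include "Patient who during the study begins to consume any type of supplement (vitamins, minerals, omega 3", with no restriction to one arm.

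**The concern.** Both groups receive the same nutrition talk, so flaxseed is meant to be what separates them, and the general objective in Section 2 concerns the effect of flaxseed consumption. If only group B is messaged every day, a second difference enters. Daily personal contact can change diet and medicine-taking, and through them glucose, HbA1c and lipids. The between-group difference could not then be credited to flaxseed alone.

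There is also a selection problem. The only place where the protocol says that patients are asked about new supplements is the daily contact. If that contact runs in one arm, the event that removes a patient is actively sought in group B and not, by any stated route, in group A. Eliminations could then differ by arm because of how hard each arm was watched. Medication changes and symptoms would have the same imbalance. No later analysis can recover answers that were never sought in group A.

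**Working it through.** The protocol gives no number of contacts, no sample size and no power for this point, so there is no stated figure to reproduce. The check has three parts: which arm the text points to, how large the contact difference would be, and what it could do.

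**1. Which arm the text points to**

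| Points to group B only | Leaves both arms open |
|---|---|
| The stated purpose is a flaxseed reminder, and only group B has flaxseed | Phase 4 says participants, not group B |
| The next paragraph names both groups, and only for the 15-day recalls | Phase 3 names group B when it means B alone; the WhatsApp sentence does not |
| The group A description has no daily contact | All patients must have a means of contact |
| The Section 10 risk table monitors problems due to flaxseed | The daily-contact sentence in Section 10 names no arm |

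The balance favours group B only, but no sentence says so.

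**2. Number of contacts**

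Inputs: the intervention is "16 gr of flaxseed/day for three months" (Section 5), taken as 90 days; one WhatsApp contact per day; one recall per 15 days.

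- Daily contacts: 90 × 1 = 90.
- 15-day contacts: 90 / 15 = 6.
- Group B only: B has 90 + 6 = 96 and A has 6. The excess is 90 and the ratio is 96 / 6 = 16. With 92 days, B has 92 + 6 = 98 and the ratio is about 16.3.
- Both arms: 96 against 96. The excess is 0, and only the flaxseed reminder differs.

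**3. What the difference could do (illustrations on assumed inputs)**

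*Detection.* Assume full reporting, and assume that the 15-day contact also asks the question, which the protocol does not say. An episode lasting L days is current at a daily query with certainty, and at a 15-day query with probability L / 15:

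| L (days) | Daily query | 15-day query |
|---|---|---|
| 1 | 1.00 | 0.07 |
| 3 | 1.00 | 0.20 |
| 5 | 1.00 | 0.33 |
| 7 | 1.00 | 0.47 |

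This applies to short episodes. A supplement that is started and continued would be found at the next 15-day contact if the question were put there.

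*Attention.* Assume that flaxseed has no effect, that only group B is contacted daily, and that contact alone lowers HbA1c by 0.1 to 0.3 points. The chance that a two-sided 5% two-sample t test is significant, from the non-central t distribution with non-centrality shift / (SD × √(2/n)), is:

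| n per arm | SD of change 1.0 | SD of change 1.5 |
|---|---|---|
| 30 | 7% to 21% | 6% to 12% |
| 50 | 8% to 32% | 6% to 17% |
| 100 | 11% to 56% | 8% to 29% |

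The shift, the SD and n are all assumptions. If both arms are contacted alike, the contact shift is zero and the figure returns to 5%.

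**The case against.** The strongest reply is that the protocol never restricts the daily contact to group B. Phase 4 and Section 10 say participants, and every patient must be reachable. That stands: a reader might infer as fact that group B gets about 90 extra contacts, but the documents support this only as the more natural of two readings.

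Other stronger inferences also fail:
- A reader might say that the message has no content for group A even if it was meant for both arms. Only the flaxseed reminder is specific to B. The symptom check, the answering of doubts and the questions on supplements and medicines could all be put to group A.
- A reader might turn 90 and 6 into a 15-fold difference in detecting supplement starts. Asking more often does not mean finding proportionally more, and the protocol does not say that the 15-day recall asks about supplements at all.
- A reader might claim a biased adverse-effect comparison. No between-group comparison of symptoms is planned; symptoms appear as safety monitoring.
- A reader might extend unequal detection to the main outcomes. Section 5 has glucose, HbA1c and lipids measured by the laboratory in every participant at the beginning and the end, so their ascertainment is equal. Only behaviour can shift them.

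Reminders may also be a deliberate part of the intervention. That is legitimate, but the effect should then be described that way. The 15-day diet records in both arms, which the protocol means to analyse as influences on the markers, cover part of the diet pathway but not medicine-taking. Finally, group B's pamphlet on the benefits of flaxseed and the absence of any described placebo mean that matched messages would not remove every expectancy difference. They would still remove this one.

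**Conclusion.** The point holds as a gap in the protocol: it does not state whether group A receives the daily contact, and the wording leans towards group B only. On that reading the excess is about 90 contacts over three months. A between-group difference in the biochemical markers would combine flaxseed with daily attention, and supplement starts, medication changes and symptoms would be followed more closely in one arm, so eliminations could differ by arm. On the other reading the excess is zero.

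The contact count rests on a 90-day period and on the B-only reading. The size of any effect on HbA1c cannot be taken from the protocol; the 6% to 56% range rests wholly on assumed inputs and shows only that the risk could be small or large. The change is worth making because it costs little and cannot be replaced by analysis afterwards.

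**What to change.** State in Phase 4, and in the same terms in Section 10, which groups receive the daily contact. Then:

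1. **Minimum.** Ask both groups the same symptom, supplement and medication questions on the same schedule, at least at the 15-day recalls that both already receive. Apply the supplement elimination criterion, and make any between-group comparison of these items, only on those common answers. Daily safety contact in group B can continue alongside.
2. **Preferred addition.** Send group A a neutral message at the same frequency as group B, with the flaxseed reminder as the only added line for B.
3. **If daily contact stays in group B only.** Describe the estimated effect in the objectives and the report as that of flaxseed plus daily contact.

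The cost is a wording change and a few extra questions or messages for group A. The downside is a slightly more intensive control condition than the one now described, which is why the matched message is a preference and the common questions are the minimum.

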General

- To assess the adjuvant effects of flaxseed consumption (16 g of flaxseed per day/3 months) on

Biochemical factors (glucose, glycosylated hemoglobin, total cholesterol, triglycerides, LDL cholesterol and cholesterolHDL) of adult patients (30 to 70 years) with type 2 diabetes mellitus, who attend the Nutrition outpatient clinic from the Regional Hospital of Oaxaca.

Specific Objectives

1. Describe the sociodemographic variables (age, sex, occupation, marital status) of adult patients (30 to 70 years) who suffer from type 2 diabetes, who attend the Nutrition outpatient clinic at the Regional Hospital from Oaxaca.
2. Describe the clinical characteristics (time of evolution of the disease, type of treatment, control and comor-bilities), of adult patients (30 to 70 years) who suffer from type 2 diabetes, who attend the outpatient clinic of Nutrition at the Regional Hospital of Oaxaca.
3. Assess the anthropometric variables (weight and height) of adult patients (30 to 70 years) who suffer from diabetes type 2, who attend the Nutrition outpatient clinic at the Regional Hospital in Oaxaca.
4. Evaluate the biochemical parameters (glucose, glycosylated hemoglobin, total cholesterol, triglycerides, LDL cholesterol and HDL cholesterol) of adult patients (30 to 70 years) suffering from type 2 diabetes, who attend the Nutrition outpatient clinic of the Regional Hospital of Oaxaca, prior to the consumption of flaxseed and three months after regular consumption of flaxseed.

5. Apply a nutritional intervention to two groups: Group A) Teaching the healthy eating plate and Group B) Teaching healthy eating dishes and indicating flaxseed consumption.
6. Evaluate the effect of flaxseed consumption on biochemical markers (glucose, glycosylated hemoglobin, Total cholesterol, triglycerides, LDL cholesterol and HDL cholesterol of adult patients (30 to 70 years) suffering from type 2 diabetes, who attend the Nutrition outpatient clinic at the Regional Hospital in Oaxaca.
7. Analyze the most effective possible combinations (pharmacological + non-pharmacological) for the treatment of Adult patients (30 to 70 years) who suffer from type 2 diabetes, who attend the Nutrition outpatient clinic at the Regional Hospital of Oaxaca.

4. Justification

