The nutritionist will take the participant's weight and height and record them at the beginning and end of the study.

Specialized nurses will take 5 milliliters of blood in the clinical laboratory area of the Regional Hospital

from the of Oaxaca and a clinical chemist professional will assess the biochemical parameters glucose, hemoglobin glycosylated, total cholesterol, triglycerides, LDL cholesterol and HDL cholesterol of each participant, at the beginning and at the end of the study (after three months of intervention, consuming 16 g of flaxseed/day).

The effect of flaxseed consumption on biochemical markers (glucose, hemoglobin) will subsequently be evaluated.

glycosylated, total cholesterol, triglycerides, LDL cholesterol and HDL cholesterol and the possible combinations will be analyzed (pharmacological + non-pharmacological) most effective for the treatment of type 2 diabetes.

6. Selection criteria and description of participants.

Selection criteria

Patients living with type 2 Diabetes Mellitus and who come with fasting blood glucose greater than 140 and hemoglobin glycosylated greater than 6.5%, who are beneficiaries who attend the Nutrition outpatient clinic of the Hospital-Regional "Presidente Benito Juárez" diagnosed at most one year ago and who agree to participate in the study, age between 45 and 65 years with regular attendance at the outpatient clinic, minimum of 3 consecutive months.

7. Methods of selection and inclusion of participants in the study.

Phase 1. Sample recruitment.

The convenience sample will be recruited by self-selection: patients who attend the nutrition outpatient clinic that meet the inclusion criteria, they will be invited to participate in the study. After giving them all information, those who wish to participate will sign the legal informed consent for participation.

Phase 2. Case randomization procedure.

Patients who sign the informed consent will be assigned a group according to the following: in the case

If you have an even number in your file, you will be part of the control group (A), and if you have an odd number, you will be part of intervention group B.

Group A.

They will be given verbal instructions to continue with the treatment established by the treating physician, and they will be provided with nutritional guidance with the help of the healthy eating plate.

Group B.

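### The only test and threshold the protocol fixes are for change within each group, which cannot isolate flaxseed; the group B versus group A contrast is left open.

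*Protocol*

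**What the plan says.** Section 7, Phase 5 (Data analysis) has two relevant statements. The first is general: "for group comparisons different tests will be performed depending on the nature of the variables". It names no test, does not say whether change or the month-3 value is compared, and carries no threshold. The second is specific: baseline is compared with "the values measured after 3 months in each group will be performed using the paired t test", and p < 0.05 is given as the end of that sentence. No other section fixes an analysis of group B against group A.

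The aims point to a contrast between arms. The general objective concerns the adjuvant effects of flaxseed on six biochemical markers. Specific objective 5 defines the groups as A, "Teaching the healthy eating plate and Group B) Teaching healthy eating dishes and indicating flaxseed consumption". Specific objective 6 is to "Evaluate the effect of flaxseed consumption on biochemical markers".

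Phase 2 shows what the arms share. For the control arm: "They will be given verbal instructions to continue with the treatment established by the treating physician, and they will be provided with nutritional guidance". Group B gets the same instruction on established treatment, and "they will be given nutritional guidance with the help of the healthy eating plate and they will be provided with a pamphlet" on how to take flaxseed.

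**The concern.** A paired test in group B asks whether the markers moved over three months. It does not ask whether they moved more than they would have without flaxseed. Finding B significant and A not significant does not answer that either, because neither test compares the arms.

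Change in both arms is plausible on the protocol's own evidence. Patients enter on high values (fasting glucose above 140, HbA1c above 6.5%), so regression to the mean is expected in both groups, and both receive nutrition guidance. Section 4 says of one cited trial: "They concluded that in the 3 groups there was a reduction in blood glucose", and one of those groups had no flaxseed. That trial used a calculated diet, so it supports the plausibility of shared change, not its size. Section 4 reports another cited trial by its HbA1c reduction relative to control, which is the contrast that Phase 5 leaves open.

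The Summary foresees offering flaxseed in place of or alongside drug treatment if results are positive. What counts as positive therefore has to be the difference between arms.

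**Working it through.** **What each test estimates.** Let s be the mean change common to both arms (guidance, continued treatment, regression to the mean) and f the flaxseed effect.

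- Paired test in A: tests s = 0.
- Paired test in B: tests s + f = 0.
- B minus A: (s + f) − s = f, if the arms are otherwise comparable.

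Only the last answers objective 6. This step needs no numerical assumption.

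**Inputs for the illustration.** The protocol states no sample size, SD, effect size or power, so it has no figure to reproduce. Assumed:

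- n = 30 per arm. The cited trials in Section 4 had 30 per group, or 57 patients in two groups.
- Two-sided 0.05. The protocol does not state sidedness.
- f = 0.
- Shared standardised change d = mean change / SD of change, mainly 0.2 to 0.5.

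**Formula.** The power p of the paired t test comes from the noncentral t distribution with n − 1 degrees of freedom and noncentrality d√n. For n = 30 this is 0.2 × 5.477 = 1.095 at d = 0.2, and 0.5 × 5.477 = 2.739 at d = 0.5. With independent arms and f = 0, the probability that B is significant and A is not is p(1 − p).

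| d (n = 30) | B significant, p | B significant, A not: p(1 − p) |
|---|---|---|
| 0.1 | 0.083 | 0.076 |
| 0.2 | 0.185 | 0.151 |
| 0.3 | 0.355 | 0.229 |
| 0.4 | 0.563 | 0.246 |
| 0.5 | 0.754 | 0.186 |
| 0.8 | 0.989 | 0.011 |

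The second column peaks at 0.250, at d = 0.37.

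**Sensitivity to n, d from 0.2 to 0.5.**

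| n per arm | B significant | B significant, A not |
|---|---|---|
| 20 | 0.136 to 0.565 | 0.117 to 0.250 |
| 28 | 0.175 to 0.723 | 0.145 to 0.250 |
| 50 | 0.284 to 0.934 | 0.062 to 0.250 |

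**Between-arm test on the same null trials.** Simulation with 20,000 runs per scenario, n = 30 per arm, comparable arms, and baseline to month-3 correlation of 0.5, 0.7 or 0.8:

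- ANCOVA rejects in 0.047 to 0.052.
- Among trials where B is significant, ANCOVA rejects in 0.040 to 0.106.
- Among trials where B is significant and A is not, ANCOVA rejects in 0.084 to 0.127.

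A two-sample t test on change scores also holds its level: 0.046 to 0.053 for n = 20 to 50 and d = 0 to 0.5.

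**The reverse error.** With a real effect of 0.8 SD of change and a shared change of 0.5 SD, both arms are significant in 0.753 to 0.756. The pattern B significant, A not appears in only 0.244 to 0.247. ANCOVA detects the difference in 0.888 to 0.938.

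**The case against.** The strongest reply is that this is an omission a statistical analysis plan would fill. Phase 5 does announce group comparisons, and the plan that may name the test is not at hand. It is right that a missing between-group method alone would be no finding, and it would be wrong to say that no group comparison is planned. But the protocol goes further than silence. It commits to one test and one threshold and ties both to within-group change. A later plan naming a between-arm test would leave that sentence standing, and the choice between the two open.

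Second, the paired test has a purpose. Specific objective 4 asks for the markers before flaxseed and after three months, and a paired comparison addresses that. This stands, and it is why the paired changes should stay. Objective 4 asks for evaluation and does not require a significance test, so reporting the changes descriptively still serves it.

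Third, the protocol states no rule that a significant group B, or B significant and A not, means flaxseed works. That is true. The percentages above therefore measure what follows if the only specified test is read as the answer; they are not an error rate of a declared rule. They also rest on assumed inputs: at 30 per arm the discordant pattern runs from 1% to 25% as d varies. The argument that the paired test estimates the wrong quantity does not depend on them.

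Fourth, ANCOVA is not the only valid choice. This also stands: a t test on change keeps its level too.

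**Conclusion.** The concern holds. The protocol attaches its only named test and its only threshold to a contrast that cannot separate flaxseed from what both arms receive, while the contrast needed for the general objective and objective 6 is unspecified. This should be fixed.

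The reasoning follows from the text alone. Its size is illustrative, resting on 30 per arm, a two-sided 0.05 level, otherwise comparable arms and a shared change of 0.2 to 0.5 SD. Under those assumptions a useless supplement would show a significant paired change in group B in 19% to 75% of trials, against about 5% for a direct comparison. The pattern of paired results can also miss a real effect when both arms improve.

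**What to change.** Add to Phase 5, in these or similar terms: *The effect of flaxseed is the group B minus group A difference at 3 months, estimated by ANCOVA of the month-3 value on group, adjusted for the baseline value of the same marker, with a 95% CI. The two-sided threshold p < 0.05 applies to this difference. Within-group paired changes are reported descriptively.*

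**Cost.** Two or three sentences and no new measurements, since Section 5 already has each marker measured at the beginning and end of the study in every participant. The downside is precision: a difference between arms is harder to detect than a change within one. At an assumed 30 per arm, ANCOVA detects a difference of 0.5 SD of change in 51% to 59% of trials.

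**Limits.** The change does not remove possible bias from allocation by even or odd file number (Phase 2), or from eliminating patients who stop flaxseed (Elimination criteria). Nor does it settle multiplicity. Six markers are listed with no primary, and six independent tests at 0.05 would give 1 − 0.95⁶ = 26% chance of at least one false positive. The present plan already has that gap and the fix does not widen it. Each of these needs its own change.

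### The elimination rule for incomplete forms can drop an allocated participant whose laboratory results are complete

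*Protocol*

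**What the plan says.** Protocol section 7, under Elimination criteria, has the entry "Data collection instrument with incomplete items". It stands beside voluntary withdrawal, surgery, starting a supplement and stopping flaxseed. It does not define the instrument, set a threshold, confine itself to endpoint fields or provide for recovering a missing item.

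The endpoints come from the laboratory. Section 5 states: "Specialized nurses will take 5 milliliters of blood in the clinical laboratory area of the Regional Hospital". It adds that "a clinical chemist professional will assess the biochemical parameters glucose", HbA1c and the four lipid measures, "at the beginning and at the end of the study (after three months of intervention, consuming 16 g of flaxseed/day").

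Other data come from forms. Section 5 describes a clinical history that records age, sex, occupation, marital status and disease characteristics. The summary in section 1 is broader: there the clinical history also covers weight, height and the six markers. Section 7, Phase 4, adds the dietary forms: "Both groups will be given a 24-hour recall and a food frequency questionnaire", repeated every 15 days. Their role is explanatory: "each nutrient will be used as a nutritional variable that can influence the control of the biochemical markers".

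Section 7, Phase 5, compares start and three-month values, and this "in each group will be performed using the paired t test".

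**The concern.** Whether a glucose, HbA1c or lipid value exists depends on a blood sample, not on whether someone filled in an occupation or a portion size. A rule that eliminates on form completeness can therefore discard valid endpoint pairs in order to protect descriptive or explanatory variables.

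Two things are at stake. The first is precision, because usable pairs of measurements are thrown away. The second is selection after allocation. Completing forms fully plausibly goes with motivation and attention to diet, which plausibly also affect glucose and lipids. The participants who remain may be more compliant than those allocated. If completeness also differed by group, the comparison between groups would be distorted.

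The open wording adds a practical problem: two people applying the rule could reasonably eliminate different participants.

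**Working it through.** **Inputs**

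- Follow-up: three months ("16 gr of flaxseed/day for three months", section 5), taken as about 90 days.
- Dietary forms: two per round, one round every 15 days, both groups (section 7, Phase 4).
- Rounds: 90 / 15 = 6, or 7 if a baseline round is added.
- Forms per participant: 2 × 6 = 12, or 2 × 7 = 14.
- Chance that a form has an incomplete item: not given in the protocol. Assumed values are 1%, 2% and 5%.

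The protocol states no rate of incomplete forms, so there is no figure of its own to reproduce.

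**Step 1. What can trigger the rule under each reading**

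- *Clinical history only, as described in section 5.* A blank marital status or occupation meets the rule, although both blood samples may be complete.
- *Clinical history as described in section 1, carrying the marker values.* A blank may then be a missing marker. That participant cannot enter the paired test for that marker in any case. Elimination would still remove the other five markers, and a blank sociodemographic item would still trigger the rule.
- *All data-collection forms, including the fortnightly dietary ones.* One blank item in any of 12 to 14 forms meets the rule.

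Under every reading, a participant with complete laboratory results can be eliminated. Only the frequency differs.

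**Step 2. Illustrative size**

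With chance p per form, k forms that count, independence between forms and no recovery of missing items:

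share eliminated = 1 − (1 − p)^k

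| Assumed p | k = 1 | k = 12 | k = 14 |
|---|---|---|---|
| 1% | 1% | 1 − 0.99^12 = 11.4% | 1 − 0.99^14 = 13.1% |
| 2% | 2% | 1 − 0.98^12 = 21.5% | 1 − 0.98^14 = 24.6% |
| 5% | 5% | 1 − 0.95^12 = 46.0% | 1 − 0.95^14 = 51.2% |

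**Step 3. How far the upper figures can be trusted**

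Incomplete forms probably cluster in the same people. Positive correlation lowers the share; in the extreme, where the same people leave every form incomplete, it falls back to p. Recovering missing items lowers it further. The columns for 12 and 14 forms are therefore upper illustrations, and the column for one form is what the narrow reading gives.

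**The case against.** The strongest reply is that the rule names one instrument, in the singular, and that the protocol names the 24-hour recall and the food frequency questionnaire explicitly when it means them. On that view the instrument is the clinical history, and losses of 11% to 51% do not arise. This stands as a limit on size: a reader might infer that one blank item on any of 12 to 14 forms certainly eliminates the participant, and the text does not establish that. It does not rescue the rule, because a blank marital status would still remove someone with complete blood results.

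A second reply is that section 1 puts the marker values in the clinical history, so some incomplete items would be missing endpoints. That also stands. It would be too strong to say that every elimination under this rule is unrelated to the endpoint, or that all of the loss is avoidable. Analyses that use nutrients as explanatory variables also need the dietary data.

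A third reply concerns bias. A reader might infer that group B has more contact with the team, completes more forms and so loses fewer people. The protocol describes daily contact with participants generally; only the flaxseed reminder is specific to group B. Both groups get the same dietary forms on the same schedule. Patients who cannot read or write are excluded, which narrows any schooling effect. Unequal loss is a possibility, not something the document shows. Daily contact might also allow missing items to be recovered, although the protocol does not provide for this.

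Finally, missing-data handling is often left to an analysis plan, and none is shown here. That does not answer the point, because the protocol itself already fixes elimination as the consequence.

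**Conclusion.** The concern holds in a limited form. The criterion is badly fixed: with no defined instrument, no threshold and no restriction to endpoint fields, it can remove a participant after allocation despite complete laboratory results at both times. That conclusion needs no assumption about rates and holds whichever form is meant.

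The size is unknown. It is 1% to 5% if one form counts and up to about 11% to 51% if 12 to 14 independent dietary forms count and nothing is recovered. Both ranges rest on assumed per-form rates of 1% to 5%. Selection towards more compliant participants is plausible. The documents do not support going further and claiming a bias between groups.

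**What to change.** Delete this entry from the elimination criteria in section 7. In its place, state that:

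- an incomplete item on any form is treated as missing for that variable only; and
- an incomplete item does not by itself remove a participant from the analysis of any marker measured at both the start and three months, and the participant is analysed in the allocated group.

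Requiring both measurements fits the paired test. The words *by itself* keep the change to this one rule; the other elimination criteria are a separate matter and are left as they stand.

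The cost is a short wording change, with no effect on visits, samples or treatment. The small downside is that dietary summaries and diet-adjusted analyses will rest on fewer participants than the marker analysis, so their denominators should be reported separately.
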